Patients randomized to the control arm of the study will receive usual care only. Patients in the control group will attend their normal clinic visits throughout the first three months of the study as they normally would, however, they will not receive any of the four digital health technologies above and their healthcare team will receive no additional information from any of these products.

Patient Follow-Up and Data Collection

All subjects will be enrolled in the study for a period of 6 months. The first three months will involve active clinic management, and subjects will be seen every 2-3 weeks as clinically indicated for an in-person visit as they normally would outside the research paradigm. Between visits, data regarding device usage, withdrawal rates, and device-generated health data described above will be passively collected from patients in the intervention arms of the trial and stored on a secure HIPAA-compliant database created by Medullan. During clinic visits, patients will also have the opportunity to meet with a study coordinator, who will administer surveys assessing device usability and user satisfaction (for those patients in the intervention groups only), as well as the KCCQ, health literacy and technology questionnaires, and medication adherence surveys (for all patients in the study, regardless of randomization status) to assess changes from baseline.

Once patients have "graduated" from the clinic, they will be followed for the final three months of the study via monthly phone calls from the study team. During this time, passive data collection from devices will continue. At 6 months, subjects will be asked to complete the final surveys appropriate to their randomization group either electronically or via telephone with one of our study coordinators.

Overview and Timeline of the Patient Experience

Day 0

- Patients who have passed initial screening will be approached by site study coordinators at a clinic visit (or via phone call/text messaging) regarding their interest in study participation.
- Study coordinators will describe, in detail, the study protocol with all interested patients, and patients will be asked to provide e-consent via a hippa-compliant, secure website set up for the purpose of the study, after all questions have been adequately answered.
- Consented patients will be asked to fill out a series of surveys and questionnaires used to collect baseline data for the study, including:

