The following pre-specified secondary outcomes will be measured to determine the effect of the various technologies on patient outcomes, quality of patient care, clinical efficiency, and both patient and provider satisfaction with the products.

	le l	Patient Outcomes			
	Outcome	Measure	Data Storage		
	Hospital Admissions	Epic, Ping	RedCap (Yale)		
		Rates of prescribing and dosing of beta			
	Guideline directed medical therapy	blockers, ACEi/ARBs, spironolactone (via	RedCap (Yale)		
• • • • • • • •		Surescripts)			
Adverse Events	ED visits	Hospital records	RedCap (Yale)		
	Mortality	Hospital records	RedCap (Yale)		
	Clinic no show rates	Medical records	RedCap (Yale)		
	AKI/AKD Development	Medical records	RedCap (Yale)		
	Satisfaction with device/technology	NPS score via post-study survey	HIPAA-compliant dashboard (Medullan)		
11 h 11	Frequency of use (overall and feature level)	Post-study survey	HIPAA-compliant dashboard (Medullan)		
Usability	Content rating	Post-study survey	HIPAA-compliant dashboard (Medullan)		
	Perceived impact	Post-study survey	HIPAA-compliant dashboard (Medullan)		
	· ·	linician Outcomes			
	Outcome	Measure	Data Storage		
	Amount of intravisit contact	Telephone logs in medical record			
	Number of clinic visits	Medical records			
Clinical Efficiency	Time devoted to patient care	Number of chart openings per patient	RedCap (Yale)		
	Provider assessment of global disease severity	Post-study survey			
Satisfaction	Effect on workload and efficiency	Post-study survey			
		tics of Digital Health Products			
	Outcome	Measure	Data Storage		
Completion of subject enrollment	Number of enrolled patients				
	Number of incomplete enrollments				
Completion rate of baseline assessments	Number of complete and incomplete aseessments				
400000000000000000000000000000000000000	Time to complete initial assessments				
Completion of digital health product set-up	Number of complete and incomplete product set-ups				
product set-up	Number of products that completed initial data sync				
Subject drop-off rates	Percent of patients with last screen assessed in session	Continuous data collection via product	HIDAA compliant dackhoard (Modullan)		
	Number of active (>1 login per week) patients per week	databases	HIPAA-compliant dashboard (Medullan)		
	Average number of logins per week				
	Number of patients without logins per week				
Device usage	Statistic for each session (time of day, day of week,				

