(Descriptive	number of page views, origin of login (direct, email))				
(Descriptive statistics)	number of page views, origin of login (direct, email)) Average number of interactions				
· ·					
• •	Average number of interactions				
· ·	Average number of interactions Average number of daily check-ins				
· ·	Average number of interactions Average number of daily check-ins Number of patients not using product per week				

We will also perform prespecified secondary analyses to determine the above primary and secondary outcomes at day 180, to determine if outcomes improve once clinic visits end.

An additional secondary analysis will assess the heterogeneity of the effect of each product across clinics.

5. Genetic Testing N/A 🛛

6. **Subject Population:** Provide a detailed description of the types of human subjects who will be recruited into this study.

This study will enroll adult patients attending one of the nine clinics located within YNHHS specializing in the treatment of heart failure, for management of congestive heart failure. See inclusion and exclusion criteria below.

7. **Subject classification:** Check off all classifications of subjects that will be specifically recruited for enrollment in the research project. Will subjects who may require additional safeguards or other considerations be enrolled in the study? If so, identify the population of subjects requiring special safeguards and provide a justification for their involvement.

□Children	🗆 Healthy	□Fetal material, placenta, or dead fetus
□Non-English Speaking	Prisoners	Economically disadvantaged persons
Decisionally Impaired	Employees	□Pregnant women and/or fetuses
□Yale Students	□ Females of childbearing pote	ential

NOTE: Is this research proposal designed to enroll children who are wards of the state as potential subjects? Yes □ No ⊠

8. Inclusion/Exclusion Criteria: What are the criteria used to determine subject inclusion or exclusion? Inclusion Criteria:

- 1. Adults \geq 18 years and < 80 years of age
- 2. Enrolled in a YNHHS clinic specializing in heart failure treatment
- 3. Diagnosed with congestive heart failure (CHF) (preserved ejection fraction (HFpEF) or reduced ejection fraction (HFrEF)) with or without diabetes
- 4. Within one month of a clinic visit

Exclusion Criteria:

- 1. Class IV heart failure
- 2. Stage 4 or end stage renal disease (eGFR < 30)
- 3. Recipient of a heart transplant or ventricular assist device
- 4. Under hospice care
- 5. Dementia

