The principal investigator is responsible for monitoring the data, assuring protocol compliance, and conducting the safety reviews bi-monthly. During the review process the principal investigator will evaluate whether the study should continue unchanged, require modification/amendment, or close to enrollment.

The principal investigator or the Institutional Review Board (IRB) have the authority to stop or suspend the study or require modifications. We will conduct an internal interim analysis at 50% recruitment to assess for efficacy, as described below.

This protocol presents minimal risks to the subjects and Unanticipated Problems Involving Risks to Subjects or Others (UPIRSOs), including adverse events, are not anticipated. In the unlikely event that such events occur, Reportable Events (which are events that are serious or life-threatening and unanticipated (or anticipated but occurring with a greater frequency than expected) and possibly, probably, or definitely related) or Unanticipated Problems Involving Risks to Subjects or Others that may require a temporary or permanent interruption of study activities will be reported immediately (if possible), followed by a written report within 5 calendar days of the Principal Investigator becoming aware of the event to the IRB (using the appropriate forms from the website) and any appropriate funding and regulatory agencies. The investigator will apprise fellow investigators and study personnel of all UPIRSOs and adverse events that occur during the conduct of this research project through regular study meetings and/or via email as they are reviewed by the principal investigator. The protocol's research monitors, including study sponsors, funding and regulatory agencies, and regulatory and decision-making bodies will be informed of all adverse events within 5 days of the event becoming known to the principal investigator.

d. For multi-site studies for which the Yale PI serves as the lead investigator: N/A

13. Statistical Considerations: Describe the statistical analyses that support the study design.

Baseline comparisons across the study arms will be conducted with chi-square tests for categorical variables, applying the Maentel-Haenszel correction for stratification by clinic site. Continuous variables will be compared using the Van-Elteren test for continuous, non-parametric variables and stratified t-tests for normally distributed variables.

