The study was designed to provide adequate power to detect a clinically significant change in the primary outcome measure, the score on the Kansas City Cardiomyopathy Questionnaire.⁸

The 23-item questionnaire has been validated in multiple heart failure populations, and quantified the physical limitations, symptoms, self-efficacy, social interference, and quality of life associated with living with heart failure. The KCCQ composite score can theoretically range from 0 - 100 (with 100 being the best possible score) and a change of 10 points has been determined to be the minimum clinically important difference. Within a given patient, the score is quite stable in the absence of clinical changes, with a within-patient standard of deviation of 11.8 for patients with no change in clinical status.⁹

In order to detect the minimum clinically important difference of a 10-point improvement in the KCCQ, we would need to enroll 40 patients in each arm of the trial across all centers to provide 90% power at an alpha threshold of 0.017. This gives a total of enrollment of 160. Given uncertainties around the intraclass correlation coefficient (assumed to be 0.10 here and reflecting the overall efficacy of each individual clinic) we will inflate the target sample size to 200, or 50 per arm of the trial. The lower alpha threshold represents a bonferonni correction that provides statistical power to test multiple comparisons – each of the 3 digital health interventions against the control intervention. We will attempt to balance recruitment across the centers with a per-center target of 5 individuals per trial arm.

An interim analysis will be completed at 50% enrollment. We will stop the trial for efficacy for a p value threshold of < 0.0006. Given the interim analysis, the threshold p-value for statistical significance at the end of the trial will be 0.016.

The primary analysis will be a mixed effects model comparing change in KCCQ over time in the intervention group versus the control, without accounting for a center-by-treatment interaction. In secondary analyses, we will model that interaction to determine if certain interventions are uniquely effective in certain centers.

Secondary and exploratory analyses will examine the outcomes listed above using the same procedure applied to baseline variables for outcomes assessed at one time point, and using mixed-effects models for continuous outcomes assessed at multiple timepoints.

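### Single-time-point secondary outcomes are analysed with the baseline-table tests, which give p-values but no device-versus-usual-care effect estimate and no allowance for time observed

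*Combined protocol and SAP*

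**What the plan says.** Section I, item 13 (Statistical Considerations) gives secondary and exploratory outcomes two routes.

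- Outcomes measured once are analysed "using the same procedure applied to baseline variables for outcomes assessed at one time point".
- The other route is "using mixed-effects models for continuous outcomes assessed at multiple timepoints".

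The baseline procedure stands at the start of the same item. For categorical variables: "Baseline comparisons across the study arms will be conducted with chi-square tests for categorical variables", with a Mantel-Haenszel correction for clinic. For the rest: "Continuous variables will be compared using the Van-Elteren test for continuous, non-parametric variables and stratified t-tests for normally distributed variables".

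The outcomes table in item 4 lists "Hospital Admissions" (from Epic and Ping), ED visits and mortality (hospital records), and no-show rates, AKI/AKD and number of clinic visits (medical records). It gives no window, denominator or effect measure for them. Follow-up is planned to be the same for everyone: "All subjects will be enrolled in the study for a period of 6 months". A further analysis is planned "to determine the above primary and secondary outcomes at day 180". Three device-versus-control comparisons appear in the sample-size paragraph, as the reason for the Bonferroni correction. They are not repeated for the secondary outcomes.

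**The concern.** The trial asks how each of three devices compares with usual care. A baseline table asks something else, namely whether the arms look alike, and its tests serve that purpose. Carried over to outcomes they fall short in three ways.

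- **Contrast.** A chi-square across four arms rejects when any arm differs from any other. Two devices that differ from each other can produce a significant result although neither is clearly different from usual care.
- **Estimate.** None of the named tests comes with a stated risk difference, rate ratio or confidence interval. For outcomes such as admissions and mortality, in a trial sized for KCCQ, the interval is what a reader needs.
- **Exposure.** A rank test or t-test on raw counts treats a patient observed for two months like one observed for six. If patients in one arm are observed for less time, that arm shows fewer events without any benefit.

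**Working it through.** **Which outcomes fall under the rule.** The plan does not say which outcomes count as assessed once. Admissions, ED visits, no-shows and clinic visits are counts or rates from records; mortality and AKI/AKD are binary. The mixed-model route covers continuous outcomes at several time points. So the counts and binary outcomes reach the baseline-test route by elimination. Looking at them again at day 180 does not make them continuous. Neither route as written yields an event rate.

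**The plan's own figure.** Item 13 gives no figure for events. Its one sample-size figure, 40 per arm for KCCQ, reproduces: n = 2 × (2.387 + 1.282)² × 11.8² / 10² = 37.5, so 38 (39 with the t distribution), at two-sided alpha 0.017 and 90% power. Nothing below depends on it. The simulations use the final target of 50 per arm.

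**The four-arm contrast.** Assumed illustration, 50 per arm, unstratified, each test at 5%: true risks of 25% for control and 40%, 12% and 25% for the devices. The four-arm chi-square rejects about 79% of the time. The tests of the 40% and 12% devices against control reject about 36% and 40%. The omnibus result is driven largely by the two devices differing from each other.

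**Size of the exposure bias.** The documents give no event or withdrawal rates, so these are assumptions. Let a proportion d of an arm withdraw, at times uniform over the period, with events no longer captured afterwards. Mean observed time is then 1 − d/2 of the full period, and

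apparent ratio of mean counts = true rate ratio × (1 − d_device/2) / (1 − d_control/2).

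With a true rate ratio of 1:

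| Withdrawal, device v control | Apparent ratio | Type I error at nominal 5% |
|---|---|---|
| equal | 1.00 | about 5% |
| 20% v 5% | 0.90 / 0.975 = 0.92 | 5% to 6% |
| 30% v 5% | 0.85 / 0.975 = 0.87 | 6% to 8% |
| 40% v 5% | 0.80 / 0.975 = 0.82 | 8% to 13% |
| 40% v 5%, events still captured after withdrawal | 1.00 | about 5% |

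The type I errors come from simulation: 50 v 50, gamma-Poisson counts with dispersion 1, event means between 0.3 and 1.5 per patient, unstratified rank test or t-test. The higher values within a range belong to the higher event means. In the scenarios up to 30% v 5%, and at 30% v 0%, events divided by person-time gave ratios of 0.99 to 1.02, so allowing for observed time removes the bias when withdrawal is unrelated to risk.

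**The case against.** The case on the other side has real force.

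- **Event capture.** A reader might infer that unequal withdrawal will distort the admissions and ED results. The documents do not support that. These events come from Epic, Ping and hospital or medical records, not from the device or the surveys. Device use is voluntary, so stopping the device is not leaving the study, and planned follow-up is equal. If records are searched to day 180 for everyone, withdrawal causes no bias. The plan does not say whether they are, so the bias is conditional.
- **Extreme scenario.** A reader might take type I error above 10% as the expected result. It arises only at 40% v 5% withdrawal, which has no source in the documents. At 20% v 5% the inflation is slight.
- **Pairwise testing.** A reader might infer that the plan rules out device-versus-control tests for these outcomes. It does not. Van Elteren and stratified t-tests are two-sample tests, and their natural use in this trial is each device against control. That use is unstated, not excluded. The objection does not reach the categorical outcomes, where the wording points to all arms together.
- **Validity and efficiency.** With equal observation a stratified rank test is valid for skewed counts. A power gain for a count model can be shown by simulation, but it rests on an assumed large effect and on data drawn from the model being recommended. The point does not rely on it.
- **Death.** The exclusions for Class IV heart failure, hospice care and life expectancy under 6 months should make death uncommon, so it is a small part of the exposure problem.

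What remains is the choice of method: p-values only, a four-arm contrast for categorical outcomes, and no definition of time observed.

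**Conclusion.** The point holds as a matter of analysis choice. Item 13 names a procedure for these outcomes, and that procedure does not answer the trial's question for categorical outcomes, leaves the pairs open for continuous ones, and estimates nothing. This rests on the text alone, apart from the step by elimination that places admissions and ED visits under the rule.

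The bias is a conditional addition. It needs event capture that ends at withdrawal or death, and unequal loss between arms. Under those assumptions a null device would appear to lower mean counts by about 8% at 20% v 5% withdrawal, 13% at 30% v 5%, and 18% at 40% v 5%. Otherwise it is nil. The primary KCCQ analysis is not affected. Because these are secondary outcomes and the remedy is cheap, the change should be made, but the trial's main conclusion does not hang on it.

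**What to change.** Restrict the chi-square, Van Elteren and stratified t-tests to the baseline table. For secondary outcomes, prespecify each device versus control with a 95% confidence interval:

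- **Counts** (admissions, ED visits, no-shows, clinic visits): rate ratio from negative binomial regression with clinic in the model and log observed time as offset.
- **Binary outcomes, including mortality:** clinic-stratified Mantel-Haenszel risk difference, with an exact method if events are rare.
- **Continuous outcomes measured once:** regression with clinic.

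State that record-based events are counted over fixed 90- and 180-day windows for all randomised patients whatever their device use, and that observation ends only at death or at withdrawal of consent to record access. List which outcomes belong to which route.

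The cost is SAP wording, a little more modelling and an exact fallback. Last-observed dates are needed in every arm. The documents do not show that these are held: the Patient Follow-Up section mentions withdrawal data for the intervention arms only. The monthly calls made to all arms after day 90 could supply last-contact dates for that period. The offset does not correct withdrawal that is related to risk, nor does it settle death as a competing event. Complete record capture is therefore the stronger protection.

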While patients are typically followed for approximately three months in several of these heart failure specialty clinics, this is not always the case. Even when patients have continued visits past the three month point, patients may still not have optimized care. We will reach out to any eligible patient within one month of a visit to the clinic, regardless of the length of time they have been attending clinic visits. Should we not enroll a patient during this initial call, we will continue to attempt to enroll either until a patient declines consent or until they are no longer within a month of a clinic visit.

Subject Randomization and Intervention

At this point, all consented patients will be enrolled and randomized, via a stratified permuted block randomization scheme, to one of the 4 study arms. An independent statistician will create randomization lists stratified by clinic.

Our study flow is as follows:

Three of the four study arms will be intervention groups where patients will be randomized to receive one of three digital health devices or experiences designed to enhance patient care, reduce symptoms and improve disease management, provide health coaching, and/or detect abnormalities in patients living with CHF, and overall improve the quality of life for this patient population.

Patients in each of these three groups will be encouraged to interact with their device on a daily basis. It is important to note that no formal protocol is being mandated for any of the devices (for example, patients will not be obligated to step on the BodyPort scale everyday as part of a specified protocol). They will be given information about the product, what information it provides, and how it can be helpful for them, and then will simply be encouraged to use it regularly, but may use it as often or as little as they like.

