SECTION IV: PROTECTION OF RESEARCH SUBJECTS

Confidentiality & Security of Data:

- 1. What protected health information (medical information along with the HIPAA identifiers) about subjects will be collected and used for the research? Name, SSN, zip code, DOB, medical record number, laboratory values, provider notes, medical procedures, medical history, medication lists, imaging/radiology results, hospital admission dates/discharges/records.
- 2. How will the research data be collected, recorded and stored?

All data collected from study coordinators from the EHR and through clinic visits and assessments/surveys will be will be entered and stored in Red Cap, Yale's HIPAA-compliant and secure data collection platform. The primary dataset will contain no PHI. We will maintain a separate "linking file" that contains all PHI and will be stored on a separate secure HIPAA-compliant central server within the Program of Applied Translational Research to limit the risk of accidental disclosure. The server is only accessible from within the Yale intranet (or via VPN remotely) and additionally requires separate logon username and password. No PHI will be included in analysis or publication. All analyses will proceed on this server alone. The linking file is being maintained for potential future linking to national databases of death and dialysis.

Medullan will collect data from the devices regarding frequency of use, user engagement and any healthrelated data and store on the secure HIPAA-compliant storage databases described in the methods above.

Information regarding the collection of the Participant data by the Vendor from the Participant and the storage of this collected data in the Vendor's solution is outlined below:

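### The yes/no prescribing part of the guideline-therapy outcome is compared without each patient's entry regimen, a valid test that gives up avoidable precision

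*Combined protocol and SAP*

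**What the plan says.** The secondary-outcome table in Section I, item 4 (Outcomes) lists guideline directed medical therapy. It gives the measure as "Rates of prescribing and dosing of beta" blockers, ACEi/ARBs and spironolactone, taken from Surescripts. The text after the table plans secondary analyses to "determine the above primary and secondary outcomes at day 180", which implies that day 90 is the main reading.

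Section I, item 13 offers two routes for secondary outcomes:

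- The first is "using the same procedure applied to baseline variables for outcomes assessed at one time point". For categorical data, the baseline procedure is "chi-square tests for categorical variables, applying the Maentel-Haenszel correction for stratification by clinic site".
- The second is "using mixed-effects models for continuous outcomes assessed at multiple timepoints".

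Neither route names a term for the patient's regimen at entry when the outcome is yes/no. Section IV, item 1 shows that the raw material is at hand, because the data collected include "medical history, medication lists, imaging/radiology results". No baseline guideline-therapy variable is defined anywhere.

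**The concern.** Being on a drug class is a state that a patient has or lacks at randomisation. Recruitment is from heart failure specialty clinics and patients may enter "regardless of the length of time they have been attending clinic visits", so entry regimens will differ between patients. Part of the day-90 prescribing rate will simply be the entry regimen carried forward.

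The Background (Section I, item 3) speaks of raising the uptake of guideline-recommended therapy, which is a change from entry. A comparison of day-90 status that ignores entry leaves all the variation in starting regimen in the error term. At 50 per arm, a chance gap in entry regimen also passes through to the day-90 estimate uncorrected. The stake is how much a small trial can say about this one secondary outcome.

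**Working it through.** **The plan's own figure.** No power or sample size is stated for guideline therapy. The only one in the plan is for the KCCQ: 2 × [11.8 × (2.387 + 1.282) / 10]² = 37.5, or 38 per arm, against the stated 40. That agrees if 11.8 is taken as the SD of the analysed outcome. It bears on this point only through the inflated target of 50 per arm, used below.

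**Which test applies.** Prescribed yes/no is categorical. Read one visit at a time, it gets the clinic-stratified chi-square. Read as a repeated binary outcome, it fits neither route, because the mixed models are limited to continuous outcomes. Either way no entry term is named. Dose, if handled as continuous and repeated, can enter a mixed model.

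**Inputs.** 50 per arm (item 13). The documents give no prescribing rate, start rate, stop rate or correlation, so these are assumptions: 70% treated at entry (b = 0.70), a proportion i of untreated patients start, and a proportion s of treated patients stop.

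**Formulas.**

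- Follow-up rate: q = b(1 − s) + (1 − b)i
- Correlation of entry and follow-up status: r = (1 − s − i) × √[b(1 − b) / (q(1 − q))]
- SE of a two-arm difference without entry status: √[2q(1 − q)/50]
- SE with linear adjustment for entry status: the same × √(1 − r²)
- Equivalent sample multiple: 1/(1 − r²)

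| Start / stop (assumed) | q | r | Variance removed (r²) | SE unadjusted → adjusted (points) | Sample multiple |
|---|---|---|---|---|---|
| 10% / 5% | 0.695 | 0.85 | 72% | 9.2 → 4.9 | 3.5 |
| 20% / 10% | 0.690 | 0.69 | 48% | 9.2 → 6.7 | 1.9 |
| 40% / 10% | 0.750 | 0.53 | 28% | 8.7 → 7.3 | 1.4 |

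First row in full: q = 0.70 × 0.95 + 0.30 × 0.10 = 0.695; r = 0.85 × √(0.2100/0.2120) = 0.846; r² = 0.716. For reference, r = 0.3 gives 9% and r = 0.5 gives 25%. More than half the variance is removed only when r exceeds √0.5 = 0.71.

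**Power illustration.** For 60% v 80% with 50 per arm and two-sided alpha 0.05, power is 59% unadjusted. At r = 0.5 the effective size is 50/(1 − 0.25) = 66.7 per arm and power is about 72%. At alpha 0.016 the figures are 41% and 55%. Larger r should not be paired with this effect. If 60% are treated at entry and 80% at follow-up, r in that arm cannot exceed √[(0.60 × 0.20)/(0.40 × 0.80)] = 0.61.

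**Chance imbalance.** The entry difference between two arms has SE √(2 × 0.7 × 0.3/50) = 9.2 points, so a gap of 10 points or more arises with probability 2 × [1 − Φ(10/9.17)], about 28% per class and comparison. With no product effect, such a gap carries forward multiplied by (1 − s − i): 8.5, 7 or 5 points in the three scenarios.

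These figures ignore clinic stratification. If clinics differ in prescribing, the planned test already captures part of what entry status would explain, and the extra gain is smaller.

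**The case against.** The strongest case against has five parts.

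1. *The size is unknown.* A reader might infer that the plan discards most of the available precision. The documents do not support that. It needs r above 0.71, and they give neither r nor start and stop rates. They also point towards change: the recruitment section says "patients may still not have optimized care", and Patient Follow-Up describes three months of active management with visits every 2-3 weeks. This stands, and is why only a range is given.

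2. *Detectable differences are easily overstated.* Holding the variance at a 70% rate gives 2.80 × 9.17 = 25.7 points, but that would mean a rate of 96%, where the variance is far smaller. With arm-specific variances, the unadjusted figure from 70% is about 22 points at 80% power and alpha 0.05 (about 25 at 0.016). Similarly, a rise from 70% to 85% caps r in that arm at √[(0.70 × 0.15)/(0.30 × 0.85)] = 0.64, so a large effect and a very high r cannot be claimed together. This stands.

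3. *The test is valid.* A reader might infer that chance imbalance biases the comparison. It does not: randomisation, itself stratified by clinic, keeps the comparison unbiased on average, and imbalance is already within the type I error. What is left is efficiency, and the accuracy of the one estimate the trial will produce.

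4. *The outcome is more than yes/no, and its timing is not spelled out.* Dose may already be covered by the mixed models. The prescribing rate might mean prescriptions issued during follow-up instead of status at a visit. This stands as a gap in definition. If each patient is classed yes/no under either definition, entry status remains a natural covariate and is still unused.

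5. *Adjustment brings its own problems.* A logistic model with clinic terms, at a target of 5 patients per arm per centre and a strong entry covariate, could meet separation. That argues for a linear risk-difference model, not against adjusting. The 3 classes × 3 products × 2 times = 18 comparisons exist under the planned test too.

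**Conclusion.** The point holds in limited form. For the yes/no prescribing outcome the plan names no analysis that uses entry status, although its own data sources can supply it. The planned comparison is valid but less precise than it could be. With 70% treated at entry and the three assumed start/stop patterns, adjustment would remove 28% to 72% of the variance, worth 1.4 to 3.5 times the sample. Heavy regimen turnover could bring this down to around 9% (r = 0.3).

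The range rests on the assumed rates, on linear adjustment with similar r in the compared arms, and on no allowance for clinic. The point concerns one of many secondary outcomes and leaves the KCCQ analysis untouched. It is worth changing because the gain costs little. The method should also be fixed before results are seen in an unblinded trial.

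**What to change.** In Section I, item 13:

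- Define prescribing status for each of the three drug classes at entry, day 90 and day 180 from Surescripts and the medication list, with the look-back window stated. The entry reading must be as at randomisation.
- For each class, estimate the difference in the proportion prescribed, each product versus usual care, at day 90 and again at day 180. Use a linear model with robust standard errors, adjusted for entry status of the same class and for clinic. A standardised logistic model with the same covariates is an alternative if it fits without separation.
- State that dose models include baseline dose.
- Tabulate new starts among patients untreated at entry, by arm, as supportive.

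The cost is extraction of baseline medication status from sources already in use, and slightly more analysis work. No extra visit, procedure or patient contact is needed.
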